7. PLANNED ANALYSIS

The format of the listings and tables will follow the standards defined in the BI corporate guideline “Reporting of clinical trials and project summaries” (3).

For End-Of-Text (EoT) tables, the set of summary statistics of continuous variables will be:

N	number of non-missing observations
Mean	arithmetic mean
SD	standard deviation
Min	minimum
Median	median
Max	maximum

For plasma concentrations as well as for all PK parameters the following descriptive statistics will additionally be calculated:

CV	arithmetic coefficient of variation
gMean	geometric mean
gCV	geometric coefficient of variation

For PK parameters the following descriptive statistics will additionally be calculated:

P10	10th percentile
Q1	1st quartile
Q3	3rd quartile
P90	90th percentile

The data format for descriptive statistics of plasma concentrations will be identical with the data format of the respective concentrations. The descriptive statistics of PK parameters will be calculated using the individual values with the number of decimal places as provided by the evaluation program. Then the individual values as well as the descriptive statistics will be reported with three significant digits in the CTR.

Tabulations of frequencies for categorical data will include all possible categories and will display the number of observations in a category as well as the percentage (%) relative to the respective treatment group (unless otherwise specified, all subjects in the respective subject set whether they have non-missing values or not).

Percentages will be rounded to integer numbers. The category missing will be displayed if and only if there actually are missing values.

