7.3.4 Safety analyses

Safety will be analysed based on the assessments described in Section [2.2.2.2](#). All treated subjects (TS, refer to Section [7.2](#)) will be included in the safety analysis. Safety analyses will be descriptive in nature and based on BI standards. No hypothesis testing is planned.

For all analyses, the treatment actually administered (= treatment at onset of AE) to the subject will be used (any deviations from the planned treatment will be discussed in the minutes of the Report Planning Meeting).

Treatments will be compared in a descriptive way. Tabulations of frequencies/proportions will be used to evaluate categorical (qualitative) data, and tabulations of descriptive statistics will be used to analyse continuous (quantitative) data.

Measurements (such as ECG, vital signs, or laboratory parameters) or AEs will be assigned to treatments (see Section [4.1](#)) based on the actual treatment at the planned time of the measurement or on the recorded time of AE onset (concept of treatment emergent AEs). Therefore, measurements planned or AEs recorded prior to first intake of trial medication will be assigned to the screening period, those between trial medication intake and end of REP (see Section [1.2.3](#)) will be assigned to the treatment period. Events occurring after the REP but prior to next intake or end of trial termination date will be assigned to 'follow-up'. In case of two or more treatments, the follow-up will be summarized according to the previous treatment. These assignments including the corresponding time intervals will be defined in detail in the TSAP. Note that AEs occurring after the last per protocol contact but entered before final database lock will be reported to Pharmacovigilance only and will not be captured in the trial database.

Additionally, further treatment intervals (analysing treatments) may be defined in the TSAP in order to provide summary statistics for time intervals, such as combined treatments, on-treatment totals, or periods without treatment effects (such as screening and follow-up intervals).

Adverse events will be coded using the Medical Dictionary for Regulatory Activities (MedDRA). Frequency, severity, and causal relationship of AEs will be tabulated by treatment, system organ class, and preferred term. SAEs, AESIs (see Section [5.2.5.1](#)), and other significant AEs (according to ICH E3) will be listed separately.

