On treatment cocktail	Cocktail	Date/time of first administration of the cocktail	Date/time of first administration of BI 730357 or date/time of first administration of the cocktail + Residual effect period (REP) (10 * 24h), whatever occurs earlier
On treatment Cocktail + BI 730357	Cocktail + BI	Date/time of first administration of BI 730357	Date/time of first administration of the cocktail + Residual effect period (REP) (10 * 24h)
On treatment BI 730357	BI	Date/time of first administration of BI 730357 or date/time of first administration of the cocktail + Residual effect period (REP) (10 * 24h), whatever occurs later	Date/time of second administration of the cocktail
On treatment Steady state BI 730357 + cocktail	BI + Cocktail	Date/time of second administration of the cocktail	Date/time of last administration of BI 730357 + Residual effect period (REP) (7 * 24h) Or 12:00 a.m. on day after subject's trial termination date, whatever occurs earlier.
Follow-up	F/U	Date/time of last administration of BI 730357 + REP (7 * 24h)	12:00 a.m. on day after subject's trial termination date

Statistical analyses of [REDACTED] PK parameters will be conducted by treatment period (cocktail vs. BI + cocktail).

More details on the technical implementation of these analyses are provided in the ADS Plan of this TSAP.

According to Section 1.2.6 of the CTP, the REP of the cocktail is 10 days. This is the period after the last dose with measurable drug levels and/or pharmacodynamic effects still likely to be present. [REDACTED]

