6.3 SUBJECT SETS ANALYSED

The following subject sets will be defined for statistical analysis:

- Treated set (TS):

The treated set includes all subjects who signed informed consent and were treated with at least one dose of study drug.

The treated set will be used for safety analyses.

- Pharmacokinetic parameter analysis set (PKS):

This set includes all subjects in the TS who provide at least one PK endpoint that was defined as primary or secondary and was not excluded due to a protocol deviation relevant to the evaluation of PK or due to PK non-evaluability (as specified in the subsection 'Pharmacokinetics' in section 7.3 in the CTP). Thus, a subject will be included in the PKS, even if he/she contributes only one PK parameter value for one period to the statistical assessment.

[figure not shown]
Descriptive and model based analyses of PK parameters will be based on the PKS. Thus, the primary and secondary analyses will be based on the PKS.

Relevant protocol deviations may be

- Incorrect trial medication taken
- Incorrect dose of trial medication taken
- Use of restricted medications

Plasma concentrations and/or parameters of a subject will be considered as non-evaluable, if for example

- The subject experienced emesis that occurred at or before two times median tmax of the respective treatment (Median tmax is to be determined excluding the subjects experiencing emesis),
- A predose concentration of BI 730357 is >5% Cmax value of that subject in the respective treatment period
- Missing samples/concentration data at important phases of PK disposition curve

The discussion of all exceptional cases and problems and the decisions on the allocation of subjects to analysis sets will be made at latest at the RPM.

Table 6.3: 1 Subject sets analysed

Class of endpoint	TS	Subject set	
		PKS	
Disposition	x		
Treatment exposure	x		
IPDs	x		
Demographics/baseline endpoints	x		
Safety parameters	x		
PK endpoints		x	

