7.2 CONCOMITANT DISEASES AND MEDICATION

Concomitant diseases will be coded according to the most recent version of Medical Dictionary For Regulatory Activities (MedDRA). Concomitant medication will be coded according to the most recent version of the World Health Organisation – Drug Dictionary.

CTP Section 7.3.4:

Previous and concomitant therapies will be presented per treatment group without consideration of time intervals and treatment periods.

Clarification: As all subjects belong to the same treatment group, previous and concomitant therapies will be presented for all subjects together.

A medication will be considered concomitant, if it

- is ongoing at the time of first study drug administration, or
- starts within one of the on-treatment analysis phases (see Section [6.1](#) for a definition of treatments and analysis phases).

Concomitant medication and drug therapies will be grouped by preferred term.

Only descriptive statistics are planned for this section of the report.

The relevance of the concomitant therapies to the evaluation of PK will be decided no later than at the RPM/DBLM.

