7.8 SAFETY ANALYSIS

The safety analyses are described in the CTP Section 7.3.4. All safety analyses will be performed on the TS.

The safety analyses will be descriptive in nature. No hypothesis testing is planned.

CTP 7.3.4:

Measurements (such as ECG, vital signs, or laboratory parameters) or AEs will be assigned to treatments (see Section 4.1) based on the actual treatment at the planned time of the measurement or on the recorded time of AE onset (concept of treatment emergent AEs). Therefore, measurements planned or AEs recorded prior to first intake of trial medication will be assigned to the screening period, those between trial medication intake and end of REP (see Section 1.2.3) will be assigned to the treatment period. Events occurring after the REP but prior to next intake or end of trial termination date will be assigned to 'follow-up'. In case of two or more treatments, the follow-up will be summarized according to the previous treatment. These assignments including the corresponding time intervals will be defined in detail in the TSAP. Note that AEs occurring after the last per protocol contact but entered before final database lock will be reported to Pharmacovigilance only and will not be captured in the trial database.

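### AE phases of unequal length (Cocktail at most 240 h, BI + Cocktail 298.5 h) are compared on crude counts of subjects with an AE, with no common window

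*SAP*

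**What the plan says.** Protocol 7.3.4 states the purpose of the safety tables: "Treatments will be compared in a descriptive way", using frequencies and proportions for categorical data and no hypothesis tests. AEs are assigned by the treatment in force at onset.

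SAP 6.1 divides the trial into four on-treatment phases, which form the columns of the AE tables. In Table 6.1: 1, Cocktail starts at the first cocktail dose and stops at the first BI 730357 dose or after 10 × 24 h, whichever is sooner. BI + Cocktail starts at the second cocktail dose and stops at "Date/time of last administration of BI 730357 + Residual effect period (REP) (7 * 24h"), or at trial termination if that is sooner. A separate Cocktail + BI phase covers any overlap between the first cocktail's residual effect period and the start of BI 730357.

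SAP 7.8.1 bases all AE analyses on the number of subjects with an AE. It gives no exposure-adjusted rate and no common observation window.

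On denominators, SAP 7 sets one rule for all categorical tables: "the percentage (%) relative to the respective treatment group (unless otherwise specified, all subjects in the respective subject set". The default in that parenthesis reads in full: "all subjects in the respective subject set whether they have non-missing values or not". SAP 7.8 adds: "All safety analyses will be performed on the TS". The treated set (TS) takes in consenting subjects who "were treated with at least one dose of study drug". SAP 7.8.1 names no denominator for the phase columns and refers further AE detail to an internal standard.

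**The concern.** A subject observed for longer has more opportunity to report at least one AE. When one column covers at most 240 h and the other 298.5 h, the crude percentage is expected to be higher in the second even if BI 730357 does nothing. The Cocktail phase can only shrink from its maximum, and the SAP provides for this by defining an overlap phase, which exists only when BI 730357 starts before 240 h. The distortion therefore runs one way, towards more AEs under Test. The same frequencies by treatment are also planned for the ClinicalTrials.gov disclosure (SAP 7.8.1).

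The denominator is a second, smaller matter. Reference always precedes Test, so a subject who leaves after Period 1 is in the TS but never enters the BI or BI + Cocktail phases. If the general default were applied literally, such a subject would still count in those columns and lower their percentages.

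**Working it through.** **Phase lengths**

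- Last BI 730357 dose: Day 6, 19:30. The second cocktail dose is on Day 1, 09:00. The difference is 5 days 10.5 h = 130.5 h, which reproduces the 130:30 printed in the Test flow chart.
- BI + Cocktail: 130.5 + 7 × 24 = 298.5 h.
- Effect of trial termination: the end-of-trial examination is on Day 14 at the earliest. Midnight after Day 14 is 14 × 24 − 9 = 327 h after the second cocktail dose, which is later than 298.5 h. The full 298.5 h therefore applies to every completer.
- Cocktail: min(time of first BI 730357 dose, 10 × 24 h), so at most 240 h.
- Smallest ratio of the two windows: 298.5 / 240 = 1.24.

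**Effect on the percentage with no drug effect**

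Assume a constant background rate that gives a proportion p of subjects with an AE in 240 h. The expected proportion in L hours is 1 − (1 − p)^(L/240).

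For p = 20%, the 298.5 h of BI + Cocktail give 1 − 0.8^(298.5/240) = 24.2%, or 3.6 of 15 subjects. The Cocktail figure depends on when BI 730357 starts. The interval between periods is redacted, so the start times below are assumptions:

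| First BI 730357 dose after first cocktail | Cocktail length | Window ratio | Cocktail | BI + Cocktail |
|---|---|---|---|---|
| 240 h or later | 240 h | 1.24 | 20.0% (3.0 of 15) | 24.2% |
| 166 h (07:00 on the morning after the Day 7 visit) | 166 h | 1.80 | 14.3% (2.1 of 15) | 24.2% |
| 143 h (the Day 7 visit itself, as a bound) | 143 h | 2.09 | 12.4% | 24.2% |

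With the full 240 h, other background levels give 10% against 12.3%, and 40% against 47.0%.

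**Common window**

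Limiting both columns to onset 0-143 h gives 1 − 0.8^(143/240) = 12.4% in each, so the difference due to window length disappears. Scheduled contacts cover the window in both periods: Reference has a visit at 143 h, and Test has contacts up to 130:30 and again at 167 h.

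Frequency of questioning is not equalised. Between 48 h and 143 h, Reference has questioning at 71, 95 and 143 h (three visits). Test has twice-daily visits, with BI 730357 doses at 58:30, 70:30, 82:30, 94:30, 106:30, 118:30 and 130:30 (seven dosing visits).

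**Denominator**

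Protocol 3.3.5 considers replacement once more than 3 subjects fail to complete, so up to 3 of 15 may be lost without it. If all 3 left before Period 2, 3 subjects with an AE would read 3/15 = 20.0% on the whole TS and 3/12 = 25.0% on those who entered the phase. If nobody leaves before Period 2, the two denominators for BI + Cocktail are the same.

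**The case against.** The windows differ because the treatments differ: a single-dose Reference is set against 13 days of BI 730357, with residual effect periods of 10 and 7 days. Ending Cocktail at the first BI 730357 dose follows the protocol's rule of assigning AEs to the treatment actually received. Safety is neither a primary nor a secondary endpoint, nothing is tested, and N is 15. At the 240 h maximum the shift is about 4 points, or 0.6 of a subject. The larger figures depend on an assumed start of BI 730357, and a constant rate after a single-dose cocktail is itself only an illustration. All of this stands, and it limits the size of the point. It does not remove it, because the crude proportions are the planned comparison and the tables carry no correction for phase length.

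A reader might also infer that AE percentages are definitely taken over all treated subjects. The documents do not establish that. The rule in SAP 7 first refers to the respective treatment group, allows exceptions, and may be meant only to stop missing values from shrinking the denominator. The statement in SAP 7.2, "As all subjects belong to the same treatment group, previous and concomitant therapies will be presented for all subjects together", concerns therapies shown without regard to period, which is the opposite of AE tables split by phase. The internal AE standard may also settle the matter. What can be said is that the text available states no denominator for the phase columns.

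A common window does not make the periods fully alike either, because AEs are asked about more often in Test after 48 h.

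**Conclusion.** The point stands for time at risk. The AE phases have unequal length by definition, by a factor of at least 1.24 for completers, and the planned crude counts carry that difference into the descriptive comparison of Test with Reference. Under a constant background rate, 20% in 240 h corresponds to 24.2% in 298.5 h. With BI 730357 starting at an assumed 166 h, the contrast is 14.3% against 24.2%.

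A reader might go further and conclude that the Test and Reference incidences are not comparable. That is too strong: the shift is modest at the 240 h maximum, and the larger values rest on an interval that cannot be checked. The incidences are better described as not directly comparable without allowing for phase length.

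The denominator is a matter of clarification. It has consequences only if subjects leave before Period 2, or if only some subjects have a Cocktail + BI phase. An all-TS denominator would act against the effect of the longer window, but nothing makes the two cancel.

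**What to change.** In SAP 7.8.1, add one supplementary AE table for Cocktail versus BI + Cocktail limited to onset 0-143 h after each cocktail dose. Add a note that AE questioning between 48 h and 143 h is more frequent in Test (visits twice daily) than in Reference (71, 95 and 143 h). The window is not cut by BI 730357 as long as Period 2 starts after the Day 7 visit of Period 1.

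In SAP 7 or 7.8.1, state that the denominator of each phase column is the TS subjects who entered that phase.

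The cost is a few sentences in the SAP and one extra table, with no change to data collection. The downside is that the supplementary table omits later AEs. They remain in the existing phase tables, which should be kept.

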7.2 CONCOMITANT DISEASES AND MEDICATION

Concomitant diseases will be coded according to the most recent version of Medical Dictionary For Regulatory Activities (MedDRA). Concomitant medication will be coded according to the most recent version of the World Health Organisation – Drug Dictionary.

CTP Section 7.3.4:

Previous and concomitant therapies will be presented per treatment group without consideration of time intervals and treatment periods.

Clarification: As all subjects belong to the same treatment group, previous and concomitant therapies will be presented for all subjects together.

A medication will be considered concomitant, if it

- is ongoing at the time of first study drug administration, or
- starts within one of the on-treatment analysis phases (see Section [6.1](#) for a definition of treatments and analysis phases).

Concomitant medication and drug therapies will be grouped by preferred term.

Only descriptive statistics are planned for this section of the report.

The relevance of the concomitant therapies to the evaluation of PK will be decided no later than at the RPM/DBLM.

7.3 TREATMENT COMPLIANCE

Treatment compliance will not be analysed as a specific endpoint.

7.4 PRIMARY ENDPOINTS

Analysis of relative bioavailability of primary endpoints $AUC_{0-\infty}$ and C_{max} of rosuvastatin, digoxin, metformin and furosemide in plasma will be performed in the PKS as defined in Sections 7.1 and 7.3.1 of the CTP. The analysis will be descriptive in nature.

There will be eight ANOVA models, as there are two primary endpoints and four drugs to be analysed.

The statistical model for the primary analysis defined in the CTP is an analysis of variance (ANOVA) model on the logarithmic scale including "treatment" as fixed effect and "subject" as random effect.

Primary PK endpoints will be assessed descriptively. The analysis of standard PK parameters is calculated according to the relevant BI internal procedures. See Sections 7.3 and 7.5.2 of the CTP for details regarding exclusion of PK parameters and plasma concentrations.

7.5 SECONDARY ENDPOINT

7.5.1 Key secondary endpoints

This section is not applicable as no key secondary endpoint has been specified in the protocol.

7.5.2 Secondary endpoint

Analysis of relative bioavailability of the AUC_{0-tz} of rosuvastatin, digoxin, metformin and furosemide in plasma will be performed in the same way as for the primary endpoints. This results in 4 ANOVA models: for rosuvastatin, digoxin, metformin and furosemide.

[figure not shown]
Additionally, the secondary PK endpoint will be assessed descriptively.

The analysis of standard PK parameters is calculated according to the relevant BI internal procedures. See Sections 7.3 and 7.5.2 of the CTP for details regarding exclusion of PK parameters and plasma concentrations.

7.6.1 Safety parameters

Safety and tolerability will be analysed as described in Section [7.8](#) of this TSAP.

7.8 SAFETY ANALYSIS

The safety analyses are described in the CTP Section 7.3.4. All safety analyses will be performed on the TS.

The safety analyses will be descriptive in nature. No hypothesis testing is planned.

CTP 7.3.4:

Measurements (such as ECG, vital signs, or laboratory parameters) or AEs will be assigned to treatments (see Section 4.1) based on the actual treatment at the planned time of the measurement or on the recorded time of AE onset (concept of treatment emergent AEs). Therefore, measurements planned or AEs recorded prior to first intake of trial medication will be assigned to the screening period, those between trial medication intake and end of REP (see Section 1.2.3) will be assigned to the treatment period. Events occurring after the REP but prior to next intake or end of trial termination date will be assigned to 'follow-up'. In case of two or more treatments, the follow-up will be summarized according to the previous treatment. These assignments including the corresponding time intervals will be defined in detail in the TSAP. Note that AEs occurring after the last per protocol contact but entered before final database lock will be reported to Pharmacovigilance only and will not be captured in the trial database.

7.8.1 Adverse Events

AEs will be coded with the most recent version of MedDRA. The analysis of AEs will be descriptive in nature. All analyses of AEs will be based on the number of subjects with AEs and not on the number of AEs.

The analysis of AEs will be based on the concept of treatment emergent AEs. That means that all AEs occurring between first drug intake till last drug intake + REP will be assigned to the on-treatment phases as defined in Table [6.1:1](#). All AEs occurring before first drug intake will be assigned to 'screening' and all AEs occurring after the last drug intake and the REP will be assigned to 'follow-up'. For details on the treatment definition, see Section [6.1](#).

AEs will be analysed based on the actual treatment at the recorded time of AE onset. Any deviations from the planned treatment will be discussed in the minutes of the RPM.

Pre-defined adverse events of special interest (AESIs) are defined in the CTP Section 5.2.5.1.4. Hepatic injury, severe infections and opportunistic and mycobacterium tuberculosis infections are considered AESIs. The investigator classifies on the eCRF whether an observed AE was an AESI or not.

According to ICH E3 (3), in addition to Deaths and Serious Adverse Events and AESIs, 'other significant' AEs need to be listed in the clinical trial report. These will be any non-serious adverse event that led to an action taken with study drug (e.g. discontinuation or dose reduced or interrupted). SARS-CoV-2 infections and AEs related to SARS-CoV-2 will also be listed.

An overall summary of AEs will be presented.

The frequency of subjects with AEs will be summarised by treatment, primary system organ class (SOC) and preferred term. AEs which were considered by the investigator to be drug related (primary endpoint) will be summarised separately. A separate table will also be provided for subjects with serious adverse events (SAEs). A table will be provided for subjects with pre-specified AESIs, summarised by SOC and PT. The frequency of subjects with AEs will also be summarised by maximum intensity, primary SOC and preferred term.

The SOC will be sorted alphabetically, preferred terms will be sorted by frequency (within SOC).

Post-hoc AESIs may be defined at a later time point and summarised separately.

For further details on summarization of AE data, please refer to "Analysis and Presentation of Adverse Event Data from Clinical Trials" (4) and "Handling of missing and incomplete AE dates" (5).

For disclosure of AE data on ClinicalTrials.gov, the frequency of subjects with non-serious AEs occurring with an incidence of greater than 5 % (in preferred terms) will be summarised by treatment, primary SOC and preferred term. The frequency of subjects with SAEs will also be summarised.

For disclosure of AE data in the EudraCT register, the frequency of subjects with AEs, the frequency of subjects with non-serious AEs with an incidence of greater than 5 % (in preferred terms) and the frequency of subjects with SAEs will be summarised. Furthermore, the total number of treated subjects by country and by age group will be summarised.

For support of lay summaries, the frequency of subjects with drug-related SAEs will be summarised by treatment, primary system organ class and preferred term.

For the subgroup of subjects with SARS-CoV-2 infection while on treatment with study drug the number of subjects with AEs, with AEs by SOC and preferred term, with AEs leading to discontinuation by SOC and preferred term and with SAEs by SOC and preferred term will be summarised.

